#### 12.4 Analysis of Secondary Endpoints

Secondary endpoints include PFS, TTP, PRO and CBR. PFS is defined as the duration of time from start of treatment to time of progression or death, whichever occurs first. Development of new disease or progression in any established lesions is considered progressive disease, regardless of response in other lesions. All subjects surviving at the time of analyses without events will be censored at their last follow-up date. PFS along with the confidence intervals will be estimated using the Kaplan-Meier method. TTP will be reported as the length of time from the start of treatment until the evidence of disease progression. Clinical benefit will be described using subject reported outcomes using PRO Numerical Rating Scale 11 as well as reporting the clinical benefit rate (CBR), defined as the proportion of subjects experiencing of objective response (CR+PR) or stable disease  $\geq$  4months.

#### 12.5 Analysis of Exploratory Endpoints

Exploratory studies will be performed post hoc, in a pre-planned manner, and will include measurement of immune correlate T cell receptor beta chain V gene family (TCRVB) for patients who underwent radiation therapy to primary or metastatic sites. All data will be summarized using descriptive statistics along with graphical illustrations. Exploratory studies will also examine circulating tumor DNA (ctDNA) when performed as standard of care.

#### **12.6 Analysis of Safety Data**

The incidence, severity and reversibility of toxicities will be performed on all subjects who receive any dose of study medication. Non-serious adverse events that occur more than 30 days after the administration of the last dose of treatment will not be included. The safety and tolerability of treatment is determined by reported AEs, physical examinations, and laboratory tests.. AEs will be summarized with the incidence and percentage of subjects with at least one occurrence of a preferred term (NCI - CTCAE Version 5 grade) will be included. The number of AEs reported will also be summarized. Causality (relationship to study drug) will be summarized separately. Duration of AE will be determined and included in listings along with action taken and outcome.

Laboratory results will be classified according to NCI-CTCAE, Version 5.0. Incidence of laboratory abnormalities will be summarized; laboratory results not corresponding to an NCI- CTCAE Version 5.0 term will not be graded. Laboratory toxicity shifts from baseline to worst grade will also be provided. The results from physical examination and vital sign measurement will be tabulated.

#### **12.7 Interim Analysis for Efficacy**

According to the two-stage design, an interim analysis will be performed after the first 9 subjects are enrolled in the trial and have response data available for analysis of the primary endpoint. If there are 2 or fewer responses in these 9 subjects, the study will be stopped. Otherwise, 20 additional subjects will be accrued for a total of 29. The study will stay open to enrollment during the interim analysis due to the rareness of the disease and lack of available treatment options, barring any unexpected safety concerns.

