### 12.2 Sample Size Justification

Simon's two-stage Optimum design will be used for the study to evaluate the primary endpoint of objective response rate (ORR, defined as CR+PR) of Tazemetostat. Assuming that with current treatment (traditional chemotherapy with doxorubicin and ifosfamide), ORR is 21% for the target study subjects (*Kroep*

*JR et al Annals Oncol 22:207-214, 2011*), the null hypothesis that the true ORR is 21% and this will be tested against a one-sided alternative. In the first stage, 9 patients will be accrued. If there are 2 or fewer responses in these 9 patients, the study will be stopped. Otherwise, 20 additional patients will be accrued for a total of 29. The null hypothesis will be rejected if 10 or more responses are observed in 29 subjects. This design yields a type I error rate of 5% and power of 80% when the true ORR is 45%.

Assuming an enrollment rate of 6-12 subjects per year per institutional experience, this protocol is expected to accrue within 2-4 years.

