### **Evaluation of Best Overall Response**

The best overall response is the best response recorded from the start of the study treatment until the earliest of objective progression or start of new anticancer therapy, taking into account any requirement for confirmation. The subject's best overall response assignment will depend on the findings of both target and non-target disease and will also take into consideration the appearance of new lesions. The best overall response will

be calculated via an algorithm using the assessment responses provided by the investigator over the course of the trial.

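### Section 12.7 waits for all nine stage-1 read-outs with enrolment open, although seven definite non-responders already settle a stop; an earlier trigger is a cheap improvement, not the repair of a design error

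*Combined protocol and SAP*

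**What the plan says.** Section 12.7 sets the trigger: "an interim analysis will be performed after the first 9 subjects are enrolled in the trial and have response data available". The rule then applied is "If there are 2 or fewer responses in these 9 subjects, the study will be stopped". The same section adds: "The study will stay open to enrollment during the interim analysis due to the rareness of the disease and lack of available treatment options", with an exception for unexpected safety concerns. It puts no cap on the number enrolled while stage 1 is pending.

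Section 12.2 and the synopsis give the same rule. If stage 1 is passed, 12.2 continues: "Otherwise, 20 additional patients will be accrued for a total of 29". On operating characteristics it states: "This design yields a type I error rate of 5% and power of 80% when the true ORR is 45"%.

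Appendix C governs when a subject's response status is final: "The best overall response is the best response recorded from the start of the study treatment until the earliest of objective progression", or the start of new anticancer therapy if that comes first. Section 12.7 gives no fixed read-out time and does not say how much follow-up counts as response data. Section 12.8 lets the safety committee recommend suspension for major concerns, but it contains no futility trigger.

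**The concern.** Nine subjects with at most two responses means at least seven non-responses. Once seven of the nine have progressed or started new therapy without a CR or PR, the other two cannot rescue stage 1. Section 12.7 still waits for them. If one has long stable disease, the wait may be long, and enrolment runs throughout.

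Subjects who enter in that interval cannot affect the stage-1 decision. They start a drug that has already failed the trial's own rule. A stage-1 stop is also a likely outcome if the drug is inactive. Version 1.5 changed the design from Minimax to Optimum, and the Optimum design is the one that minimises expected sample size under the null. A delayed stop works against that aim.

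**Working it through.** **Inputs from the plan.** Null ORR 21%, alternative 45%, one-sided test, stop at 2 or fewer of 9, reject at 10 or more of 29, accrual 6 to 12 per year (12.2, 12.7). Scans every 2 cycles, so 56 days or 1.84 months (6.1, 6.2). For timing scenarios only: median PFS of 17 weeks in MPNST on first-line chemotherapy (1.2) and median time to response of 3.9 months in epithelioid sarcoma (1.4.2). ORR values of 15% and 5% are what the protocol reports for this drug in epithelioid sarcoma (9 of 62) and in phase 1 solid tumours (2 of 43).

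**1. The stated design reproduces.** With X ~ Bin(9, p) and Y ~ Bin(20, p), P(reject) = sum over x = 3 to 9 of P(X = x) × P(Y ≥ 10 − x). This gives 0.0485 at p = 0.21 and 0.804 at p = 0.45. A full search returns the same design as the optimum. Its expected sample size under the null is 9 + (1 − 0.7115) × 20 = 14.8.

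**2. Probability of a stage-1 stop.** P(X ≤ 2) = 0.711 at 21%, 0.859 at 15%, 0.992 at 5% and 0.150 at 45%.

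**3. Same decision.** Seven non-responses in nine is the same event as two or fewer responses in nine. Declaring it early changes no decision, so type I error, power and stopping probability stay as in steps 1 and 2. This assumes the same nine subjects and the same definition of final status.

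**4. Which subject settles the stop.** With read-outs in order of entry, the seventh failure falls at subject k with probability C(k−1, 6)(1−p)^7 p^(k−7), for k = 7, 8, 9.
- At 21%: 0.192, 0.282, 0.237, total 0.711. Given a stop: 27%, 40%, 33%.
- At 5%, given a stop: 70%, 25%, 5%.

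So in a third of null stops the ninth subject decides and nothing is saved.

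**5. Common fixed read-out.** The expected settling subject is 7(0.270) + 8(0.397) + 9(0.333) = 8.06 at 21%, and 7.35 at 5%. The saving is 9 − 8.06 = 0.9 and 9 − 7.35 = 1.7 subjects. Simulation with Poisson accrual gave 0.9 to 1.0 and 1.6 to 1.7 at both accrual rates. With slow accrual and an 8-week read-out, these may be subjects 8 and 9 rather than subjects beyond nine.

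**6. Non-response final only at progression.** Assumed: Poisson accrual, exponential time to progression with a 17-week median, detection at 8-weekly scans, responders read out at 3.9 months. Mean enrolment in trials that stop:

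| Accrual per year | ORR | All nine determined | Seventh failure | Difference |
|---|---|---|---|---|
| 6 | 21% | 14.2 | 12.4 | 1.8 |
| 6 | 5% | 14.3 | 11.0 | 3.4 |
| 12 | 21% | 21.2 | 17.8 | 3.4 |
| 12 | 5% | 21.6 | 15.2 | 6.5 |

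Capping enrolment at 29 brings the largest difference to about 6.

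**7. One scan per subject is enough.** The look then comes 8 weeks after the ninth subject starts, with about 9.9 (6 per year) to 10.8 (12 per year) enrolled. That is usually before seven subjects have progressed, so the saving is about nil; a check run gave at most about 0.3 subjects.

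**8. Share of the excess recovered, at 21% under step 6.**
- Expected N as written: 0.7115 × 14.17 + 0.2885 × 29 = 18.5 at 6 per year; 0.7115 × 21.17 + 0.2885 × 29 = 23.4 at 12 per year.
- Excess over 14.8: 3.7 and 8.7.
- Recovered: 0.7115 × 1.81 = 1.3 and 0.7115 × 3.37 = 2.4, about 35% and 28%. A variant with steady accrual gave 48% and 32%.

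**The case against.** The strongest reply is that 12.7 applies the ordinary two-stage rule. Such a design does not require a stop to be declared early, and the plan openly chooses to keep enrolling and gives its reasons. This stands, and it is why the point is an improvement and not a correction. The reasons given, rarity and few options, do support enrolling while the result is unknown. They do not speak to the interval after it is certain.

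A reader might infer that 12.7 contradicts 12.2, because 12.2 makes the 20 further subjects conditional on passing stage 1. The documents do not support that: 12.7 states the open enrolment explicitly, and the error rates do not depend on it.

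A reader might also infer that late enrolment always follows, or that the timing rule accounts for most of the loss against the nominal 14.8. Neither holds. The effect needs a stage-1 stop and an early seventh failure, and step 8 shows that most of the excess comes from open enrolment itself, which the change keeps.

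The size is also open to challenge. Section 12.7 asks for response data, not for a final best response. The 17-week figure covers all first-line chemotherapy patients with MPNST, responders included, and is borrowed here for non-responders to another drug. The result must therefore be read as a range. The trial is open-label at one institution, so accumulating failures would be visible, but no written rule acts on them.

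**Conclusion.** The point holds as a low-cost improvement. As written, a trial that stops at stage 1 can enrol subjects after its outcome is fixed: about 2 to 6 per stopped trial if status is final only at progression, about 1 to 2 with a common fixed read-out, and about nil with one scan per subject. Nothing is saved in about a third of stops at an ORR of 21% with read-outs in entry order; steady-accrual runs of the progression scenario gave 36 to 40%. The timing figures are scenarios, since the protocol has no MPNST data on this drug. What is firm is the logic of the seventh failure, the stopping probability of 0.711 under the null, and the unchanged type I error (0.0485) and power (0.804). Only part of the excess over the nominal expected N is recovered.

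**What to change.** Reword 12.7, and match 12.2 and the synopsis, along these lines:

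*The stage-1 rule is applied as soon as its result is determined. Further enrolment stops when seven of the nine stage-1 subjects are definite non-responders, meaning progression, death, new anti-cancer therapy, withdrawal or loss to follow-up without a prior CR or PR. Stage 2 proceeds when three of the nine have a CR or PR. Otherwise the rule is applied when the status of all nine is known. A subject still on treatment without a CR or PR is not yet a definite non-responder.*

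State also that the nine are the first nine subjects in the primary-analysis set. Section 8.3 ties response evaluability to 75% of first-cycle doses and allows some replacement, while 12.3 counts all study patients. The tally must follow one consistent reading of both, or an early progressor could count towards the seven and yet not be evaluable.

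Once all nine statuses are final, one of the first two conditions must already be met, so the third clause is only a backstop. If the sponsor in fact intends a single early scan, that should be settled first. At an ORR of 21%, waiting for definite status would move the decision from about 10 or 11 enrolled to about 12 to 18. A single 1.84-month scan, however, would miss later responses, given a 3.9-month median time to response in epithelioid sarcoma.

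Cost: a few sentences, a running tally of nine subjects, and slightly fewer subjects for descriptive estimates in a trial that has already failed stage 1. Enrolment stays open until the decision, as now.

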## 1.2 Malignant peripheral nerve sheath tumor systemic therapy

The role of adjuvant therapies in unresectable MPNST has recently been investigated in both pediatric and adult trials. A large adult soft tissue sarcoma (STS) study evaluated the chemosensitivity of advanced MPNST and compared these results with other advanced soft tissue sarcoma histologic subtypes. Out of 2675 chemo naïve eligible STS, the outcome of 175 MPNST patients after a median follow up of 4.1 years showed response rate, median PFS and overall survival of 21% (versus 22%), 17 weeks (versus 16 weeks) and 48 weeks (versus 51 weeks), respectively. Chemotherapy regimen was an independent prognostic factor for response ( $p < 0.0001$ ) and PFS ( $p = 0.009$ ). Compared with standard first-line doxorubicin, the doxorubicin–ifosfamide regimen had the best response, whereas ifosfamide had the worst prognosis. A prospective European Pediatric Soft Tissue Sarcoma Group (EpSGG) study of MPNST patients under 21 years old showed 5-year event-free survival (EFS) and overall survival (OS) to be 52.9% (95% confidence interval, 38.1-65.8) and 62.1% (46.7-74.3), respectively. Similar to the adult series, standard ifosfamide-doxorubicin chemotherapy for unresectable MPNST rendered the best reported outcome, with a response rate to chemotherapy (partial response + complete response) in patients with measurable disease of 46%, higher than adults.

Preclinical studies have identified several novel candidate molecular targets for therapeutic intervention. Several early phase trials using these novel drugs have been conducted but to date, no targeted therapies have yet been proven effective (Table 1). Due to the limited number of therapeutic options in advanced MPNST, identification of novel drug targets and development of new treatment strategies are urgently needed.

Therapy	Molecular targets	No. of MPNST	Study design and population	Response	References
Erlotinib	EGFR	20	Phase II study in MPNST	No objective responses, 1 stable disease	72
Sorafenib	VEGFR, RAF, PDGFR	12	Phase II study in soft tissue sarcomas	No objective responses	73
Imatinib	c-KIT, PDGFR, VEGFR	7	Phase II study in 10 subtypes of sarcoma	No objective responses, 1 stable disease	74
Dasatinib	c-KIT, c-SRC	14	Phase II study in bone and soft tissue sarcomas	No objective responses	75
Alisertib	Aurora Kinase A	10	Phase II study in advanced sarcomas	No objective responses	76

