An open-label, single-arm, phase 2 trial done at 38 clinics or hospitals in France, the UK, Australia, Canada, Poland, Italy, Ukraine, Germany, and the USA using Tazemetostat 800 mg twice daily in patients with relapsed/refractory follicular lymphoma (NCT01897571). This study showed meaningful clinical activity and durability of response in patients with recurrent/refractory follicular lymphoma, with ORR pronounced in patients with EZH2 activating mutations. Late onset responses have been reported on Tazemetostat. Tazemetostat was generally well tolerated in heavily pretreated patients with relapsed or refractory follicular lymphoma. Between July 9, 2015, and May 24, 2019, 99 patients (45 in the EZH2mut cohort and 54 in the EZH2WT cohort) were enrolled in the study with median follow-up of

22 months for the EZH2MT cohort and 35.9 months for the EZH2WT cohort. The objective response rate was 69% (95% CI 53–82; 31 of 45 patients) in the EZH2mut cohort and 35% (23–49; 19 of 54 patients) in the EZH2WT cohort. Median duration of response was 10.9 months (95% CI 7.22–not estimable [NE]) in the EZH2mut cohort and 13 months (5.6–NE) in the EZH2WT cohort; median progression-free survival was 13.8 months (10.7–22.0) and 11.1 months (3.7–14.6). Among all 99 patients, treatment-related grade 3 or worse adverse events included thrombocytopenia (3%), neutropenia (3%), and anemia (2%). Serious treatment-related adverse events were reported in four (4%) of 99 patients. There were no treatment-related deaths.

In 2016, the Food and Drug Administration (FDA) granted Tazemetostat Fast Track status in 2016 for patients with relapsed/refractory DLBCL with EZH2-activating mutations. On June 18, 2020, the Food and Drug Administration (FDA) granted accelerated approval to Tazemetostat for adult patients with relapsed or refractory (R/R) follicular lymphoma whose tumors are positive for an EZH2 mutation and who have received at least 2 prior systemic therapies, and for adult patients with R/R follicular lymphoma who have no satisfactory alternative treatment options.

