#### 1.4.2 Solid tumors

There are preclinical data on impact of inhibition of EZH2 overexpression in various solid tumors, including MPNST, but degree of downstream effects is tumor dependent and overall clinical impact in terms of response rates in MPNST is unknown. Tazemetostat has been shown to have antitumor activity in preclinical malignant rhabdoid tumor (MRT) models that were negative for the INI1 protein and in phase I trials of MRT and epithelioid sarcoma. In an open-label, phase 2 basket study, patients were enrolled from 32 hospitals and clinics in Australia, Belgium, Canada, France, Germany,

Italy, Taiwan, the USA, and the UK into seven cohorts of patients with different INI1-negative solid tumors or synovial sarcoma (NCT02601950). Patients eligible for the epithelioid sarcoma cohort (cohort 5) were aged 16 years or older with histologically confirmed, locally advanced or metastatic epithelioid sarcoma; documented loss of INI1 expression by immunohistochemical analysis or biallelic SMARCB1 (the gene that encodes INI1) alterations, or both. Patients received Tazemetostat 800 mg orally twice per day in continuous 28-day cycles and primary endpoint was objective response rate per RECIST 1.1. Between Dec 22, 2015, and July 7, 2017, 62 patients with epithelioid sarcoma were enrolled in the study. Tazemetostat was well tolerated and showed clinical activity in this cohort of patients with advanced epithelioid sarcoma. Nine (15%) of 62 patients had an objective response at data cutoff (Sept 17, 2018). At a median follow-up of 13.8 months, median duration of response was not reached (95% CI 9.2 -not estimable). 16 (26%) patients had disease control at 32 weeks. Median time to response was 3.9 months. Median progression-free survival was 5.5 months (95% CI 3.4-5.9), and median overall survival was 19 months (11-not estimable). Grade 3 or worse treatment-related adverse events included anemia (6%) and weight loss (3%), without treatment-related deaths. A phase 1b/3 trial of Tazemetostat plus doxorubicin in the front-line setting is currently underway (NCT04204941).

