## 6.2 Allowable Visit Windows

Visit Name	Window
Screening	
Informed Consent	≤ 28 days prior to Cycle1 Day 1 (C1D1)
Medical History, Physical examination, Performance Status, Concomitant Medications, and Labs (CBC Diff, CMP, INR, pregnancy test)	≤ 28 days prior to Cycle1 Day 1 (C1D1)
Tibial X-Ray	≤ 180 days prior to Cycle1 Day 1 (C1D1)
Imaging (CT and PET)	≤ 30 days prior to Cycle1 Day 1 (C1D1)
All other screening procedures	≤ 7 days prior to C1D1
Cycle 1 Day 1	
Labs	Laboratory tests at screening need not be repeated if therapy starts within 72 hours of obtaining labs to assess eligibility. All others to be done ≤ 72 hours of C1D1 dosing. Labs are to be collected weekly for Cycle 1 (Days 1, 8, 15, and 22) +/- 72 hours
All other baseline procedures (which include complete physical exam, performance status, vital signs, and concomitant medication review)	Baseline procedures completed at screening need not be repeated if therapy starts within 72 hours of performing procedures to assess eligibility. All others to be done ≤ 72 hours of C1D1 dosing.
Day 1 of subsequent cycles (after Cycle 1)	
Assessments	Within 72 hours prior to dosing
Study treatment administration (dosing)	Every 28 days
Tibial X-Ray	Every 180 +/- 30 days
Tumor Assessments	Imaging every 2 cycles +/- 7 days from Cycle 1 Day 1 until disease progression or death.
End of Treatment (EOT) Procedures	Within 14 days of last dose of therapy
28-Day Safety Follow-up	28 +/- 7 days after last dose of treatment

Survival Follow-Up	Every 90 +/- 14 days
--------------------	----------------------

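### Does the stop at 2 or fewer responses in 9 cost power because Section 12.7 does not say when a subject's response status is final?

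*Combined protocol and SAP*

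**What the plan says.** Section 12.2 sets a Simon two-stage design: null ORR 21%, target 45%, stop at 2 or fewer responses in 9, otherwise enroll 20 more and reject at 10 or more of 29. It claims 5% type I error and 80% power. Section 12.7 times the look: it is "performed after the first 9 subjects are enrolled in the trial and have response data available for analysis of the primary endpoint". The stop is worded as binding. Enrollment stays open while the interim analysis is done.

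Appendix C defines best overall response as "the best response recorded from the start of the study treatment until the earliest of objective progression or start of new anticancer therapy". Section 6.2 schedules tumor assessment: "Imaging every 2 cycles +/- 7 days from Cycle 1 Day 1 until disease progression or death". With 28-day cycles the first scan falls at about week 8. Section 7.2 allows up to two years of treatment.

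On the speed of response, Section 1.4.1 says, of follicular lymphoma, "Late onset responses have been reported on Tazemetostat". Section 1.4.2 says of the epithelioid sarcoma cohort (nine responders in 62) "Median time to response was 3.9 months". It also says that the effect on response rates in MPNST is unknown.

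**The concern.** Simon's calculation treats each of the nine as a settled response or non-response. Section 12.7 does not say in so many words that they must be settled. A subject with stable disease at the first scan has response data, yet may respond later. If the look came at the ninth subject's first scan, such subjects would count against the drug under a binding rule. The 3.9-month median in epithelioid sarcoma is about twice the interval to that scan, so the possibility is not remote.

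At stake is a false futility stop. The design already stops a drug with a 45% ORR about 15% of the time; an early look would add to that, and the 80% in Section 12.2 would no longer describe the trial. In a rare disease with few options that would matter.

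**Working it through.** **1. The plan's own figures.** Inputs from Section 12.2: n1 = 9, stop at 2 or fewer, N = 29, reject at 10 or more, p0 = 0.21, p1 = 0.45.

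Power = sum over k = 3 to 9 of P(Bin(9, p) = k) × P(Bin(20, p) ≥ 10 − k). At p = 0.45:

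- k = 3: 0.2119 × 0.8701 = 0.1844
- k = 4: 0.2600 × 0.9447 = 0.2456
- k = 5: 0.2128 × 0.9811 = 0.2087
- k = 6: 0.1160 × 0.9951 = 0.1155
- k = 7, 8, 9: 0.0407 + 0.0083 + 0.0008 = 0.0498

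The total is 0.804. The same sum at p = 0.21 gives 0.0485. The chance of stopping at stage 1 is P(Bin(9, p) ≤ 2): 0.150 at 45% and 0.711 at 21%. Expected enrollment at 21% is 9 + 20 × (1 − 0.711) = 14.8. An exhaustive search under the stated limits returns this same design as optimal. The arithmetic is sound when all nine statuses are final.

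**2. An early look, without assuming a response curve.** Let g be the probability that an eventual response is visible at the look. Each of the nine is a visible responder with probability p·g, a later responder with p(1 − g), or a non-responder with 1 − p. Stop if visible responders number 2 or fewer; reject if at least 3 are visible and the eventual total of 29 reaches 10.

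| g | Power at 45% | Stage-1 stop at 45% | Type I error at 21% |
|---|---|---|---|
| 1.00 | 80.4% | 15% | 4.85% |
| 0.95 | 77.4% | 18% | 4.5% |
| 0.90 | 73.9% | 22% | 4.2% |
| 0.80 | 65.5% | 31% | 3.5% |
| 0.70 | 55.4% | 42% | 2.8% |

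The type I error only falls.

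**3. An early look with an assumed response time.** The documents give no time to response for MPNST, so the 3.9-month median (118.7 days) is borrowed. Accrual of 6 or 12 per year is from Section 12.2 and is assumed even. Subject i has been followed for L + (9 − i) × 365.25/rate days at the look, and g_i is the response-time distribution at that subject's latest 56-day scan. The curves are Weibull with shape 0.8, 1 (exponential), 1.5, 2 and 3, and lognormal with sigma 0.3, 0.6 and 1.0.

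- Week-8 look (L = 56): power 55-68% at 6 per year and 38-49% at 12 per year; exponential 59% and 39%.
- Week-24 look (L = 168): 66-80% and 58-79%. Weibull shape 2 gives 78% and 75%; exponential gives 71% and 63%.

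The week-24 spread is the informative part. With the same median, the curve alone decides whether the loss is under a point or more than 20 points.

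**4. What waiting would cost.** Suppose no subject counts as a non-responder until progression, death, new therapy or the end of assessment, so that the stop comes at the seventh definite non-responder. Progression-free survival for non-responders is taken as exponential, with a median of 17 weeks (first-line chemotherapy, Section 1.2) or 5.5 months (epithelioid sarcoma on this drug, Section 1.4.2), detected at the next scan and capped at 728 days. In 200,000 simulated trials per setting at ORR 21%, stopped trials enroll on average 2.69 or 4.19 more subjects than at a week-8 look at 6 per year, and 7.23 or 10.50 more at 12 per year. At the week-8 look 9 subjects are in at 6 per year and 10 at 12 per year. Expected enrollment is therefore:

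- 6 per year: 14.77 + 0.711 × 2.69 = 16.7, to 14.77 + 0.711 × 4.19 = 17.7
- 12 per year: 14.77 + 0.711 × (1 + 7.23) = 20.6, to 14.77 + 0.711 × (1 + 10.50) = 22.9

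At 6 per year the median futility stop comes about 21-25 months after first enrollment, and the 90th percentile at 30-34 months, against about 18 months for the week-8 look and a planned study duration of 36 months.

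**The case for a change.** The strongest case for a change is that the rule is binding and two readings of one sentence can give opposite decisions on the same nine subjects. The table in step 2 borrows nothing from another tumor, and even if eight subjects are fully mature and only the ninth has a 50% chance of showing an eventual response, power is 77.3%. Open enrollment does not rescue the drug, because only the first nine count. One sentence would settle it, and stage 2 could be confirmed as soon as three responses were seen.

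Much of this stands. The sections on sample size, primary analysis, interim analysis and replacement, and Appendix C, state no maturity rule for the nine, and the conditional arithmetic is right. What does not follow is that the plan is wrong. Section 12.7 asks for data fit for the primary endpoint, not merely for a scan. That endpoint is response by RECIST 1.1, and Appendix C keeps best overall response open until progression or new therapy. The link is implicit, but it is there. Because accrual continues during the interim analysis, there is also little pressure to look at the first opportunity.

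**Conclusion.** No change is needed. Read in the natural way, with completed best overall response for the nine, Section 12.7 delivers the stated design: 80.4% power and 4.85% type I error, assuming nine assessable subjects and a denominator of 29. The missing detail, when a stable subject counts as a non-responder, is one the study statistician can supply sensibly at the interim.

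The loss arises only if the look is taken early, which the text permits but does not require. Its size then depends on the share of responses already visible, from 77% power at 95% visible to 55% at 70%. The figures below 50% need the earliest look, the fastest accrual and a response time from another tumor, all together. The type I error does not rise in any of these cases.

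Nor would a stricter rule be free. Waiting for every status to be final keeps the stated power but moves expected enrollment at ORR 21% from 14.8 to about 17-18 or 21-23, giving up part of what an optimal design is chosen for, and delays a futility stop. A fixed minimum follow-up stops sooner but gives up power by an amount that cannot be fixed from the documents. The choice between earlier stopping and power is the sponsor's. The cost figures rest on even accrual, exponential progression times and medians that do not come from MPNST patients on this drug.
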